8.2 SAFETY ASSESSMENTS

Participant mental health referrals

We will use the mental health data collected via study outcomes to monitor participant safety. Any individuals scoring at or above the thresholds for depression recommended by [name] (6 on the PHQ-2 scale), individuals whose scores have increased beyond a threshold of more than two since baseline, or those expressing suicidal ideation, will be contacted by phone within two days and asked if they would like to avail themselves of telephone-based counseling via a local NGO providing mental health services. Given the potential for stigma around mental health concerns in the local context, this option will be presented "as a person to talk with about any concerns that are on your mind." Counseling is phone-based to improve access as many individuals cannot travel for in-person counseling. The counseling sessions will be without charge to the participant whether or not a participant decides to continue study enrollment and regardless of study arm. Our aim is to support participants in their decision of whether to participate or not, and they should not feel concerned that their study participation is jeopardized by reporting poor mental health or other crises.

Further, in rare cases when a participant indicates thoughts of suicide, self-harm, or harm to others, Mind 'N' Health has an action protocol to, first, collect relevant details on the situation for assessment and, then, initiate follow-up actions with Ghana Health Services including in-person services at local government-run health facilities. With the participant's consent, Mind 'N' Health will also work with the individual's family to facilitate access to these additional services. We will also send a study team member in person to visit any participant expressing suicidal ideation who is not able to be reached by phone within 48 hours. This study team member will offer the counseling services in person and help the individual place the call if they are interested in accessing services.

The NGO providing the counseling is well established in the area. The minimum qualification of providers is a first degree BSc. in mental health nursing. Providers include psychologists, psychology therapists, certified counselors, and guidance and counseling experts. Services are available in all local languages that participants are expected to speak.

No results of the cortisol assays will be provided as the assays will be conducted some time after the completion of the study and the results are not clinically actionable.

Adverse event identification

Given the high disease burden in Ghana, it is anticipated that some participants are likely to become ill with diseases endemic to the area (e.g., malaria, coughs) but unrelated to their participation in the study during their enrollment in the study. We also anticipate that a large number of both treated and control participants will experience depression and anxiety during their participation due to their challenging economic circumstances. It is also likely that some workplace injuries (e.g. repetitive motion injuries) occur given the nature of the work and the large number of participants. The rate of these injuries per day is expected to be comparable or lower for treated participants given that the work provided is less physically taxing than work typically found in the area. However, overall rates may be higher given the additional work provided.

Given that we do not anticipate any adverse events associated with participation, we do not aim to gather systematic data to track such events. However, two reporting options are available to participants: 1) a study "hotline" to call regarding any concerns about their participation in the study, and 2) an open-ended question on each survey administered about any concerns about their participation. Any potential AEs or SEAs reported through these channels will be conveyed from the survey staff to their managers and from the managers to the PI and site-investigator.

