2.3 RISK/BENEFIT ASSESSMENT

2.3.1 KNOWN POTENTIAL RISKS

Risks Associated with Experimental Activities

As there are no changes to the lives of control individuals except their participation in brief surveys, the risks associated with control condition are no more than minimal and are similar to the ones in participants' everyday life. Treated participants will additionally work in the cash-forwork program, facing potential psychological and physical risks.

Psychological risks - we will proactively be screening all participants (both control and treatment) for poor mental health via the twice-monthly surveys. Any individuals scoring at or above the thresholds for depression recommended by [name], individuals who scores have increased beyond a threshold since baseline, or those expressing suicidal ideation, will be contacted by phone and asked if they would like to avail themselves of telephonic counseling with counselors provided by local NGOs. Again, those thresholds are a PHQ-2 score of six or a score increase of more than 2 relative to baseline. The counseling sessions are free whether or not a participant decides to continue participating in the study. In rare cases when a participant indicates thoughts of suicide, self-harm, or harm to others, Mind 'N' Health has an action protocol to, first, collect relevant details on the situation for assessment and, then, initiate follow-up actions with Ghana Health Services including in-person services at local government-run health facilities. With the participant's consent, Mind 'N' Health will also work with the individual's family to facilitate access to these additional services.

Physical risks - The sewing work provided has some risk of injury (e.g. sticking one's finger with a sewing needle), however this risk is likely lower and certainly no more than the risks faced by these individuals in other jobs (e.g. agricultural labor, collecting firewood). Surveys will also be conducted outdoors weather permitting and many dwellings are openair. Hence, the intervention is not likely to significantly alter Covid-19 exposure.

For AEs and SEAs related to health, participants will be referred to the closest government health post or hospital, depending on the severity of the event. The costs of transportation for AEs and SEAs considered related or potentially related to study participation will be covered by the study.

Risks associated with privacy

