Regardless of whether a participant discontinues engagement with the intervention, they will be asked if they are able and willing to continue with the ongoing surveys. These surveys are an important component of our participant safety protocols as they allow us to screen and refer participants with significant signs of psychological distress (see Section 8.2). Should a participant not be available at their home for the in-person survey, we will attempt to contact them to complete a shortened version of the study instrument via phone. Notably, we collect multiple forms of contact information at enrollment to allow us to track participants who have changed their phone numbers.

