8 STUDY ASSESSMENTS AND PROCEDURES

8.1 ENDPOINT AND OTHER NON-SAFETY ASSESSMENTS

Endpoints

Surveys will be conducted at baseline and every two weeks throughout the study as well as once roughly one month following the study. The baseline and "endline" (following period 6) are conducted in-person and are longer, typically taking about 2.5 hours. All other surveys are conducted by phone, typically taking under 30 minutes. These surveys will be used to collect our primary and secondary outcomes, described in section 3 as well as measures of channels (primarily economic outcomes), and demographics. These outcomes include:

Mental Health Outcomes:

- Anxiety
 - Abbreviated Version of General Anxiety Disorder (GAD-2)
 - General Anxiety Disorder-7 (GAD-7)
- Depression
 - Abbreviated Version of Patient Health Questionnaire (PHQ-2)
 - Patient Health Questionnaire-8 (PHQ-8)
- Stress
 - Abbreviated Version of Cohen's Perceived Stress Scale (PSS-4)
 - Cohen's Perceived Stress Scale (PSS)
 - Cortisol (Participants will be asked to provide a small sample of hair to measure cortisol levels. There is no penalty for declining this request. The hair collected will be from the approximately 2 cm below the cranial bone and cutting off 2-3 strands of hair, following the hair collection study protocol developed by the Biomarker Network. The hair samples will be collected at the participant's home and analyzed in a single laboratory.)
- Wellbeing
 - Diener's Satisfaction with Life Scale
- Worry
 - Penn State Worry Questionnaire (PSWQ)

To ensure that the measures are well-understood, the translations will be validated, by a local mental health expert, [name] of the University of Ghana. Further, to ensure consistency in the translation and understanding, the survey items will be pre-recorded and played via the tablet used to conduct the survey. The enumerator will then simply key in the response provided

by the participant. Scoring of the scales above follows the standardized approaches/scoring of these measures which are all common in the existing mental health literature.

Physical health related outcomes:

- Blood pressure
- Weight
- Dietary diversity and sufficiency

Enumerators will receive extensive training in the collection of blood pressure and weight measures.

Measures of channels, such as:

- Consumption
- Labor supplied outside of the study
- Gifts/transfers
- Debts/savings
- Assets/wealth

Demographics (abbreviated list):

- Age
- Size of household
- Education

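### Under standard 0–6 PHQ-2 scoring, the referral rule's absolute trigger is the maximum score and its change trigger cannot fire from a baseline of 4 or more, so a woman scoring 5 throughout is never contacted on her score

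*Combined protocol and SAP*

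**What the plan says.** Section 8.2 sets out who is telephoned and offered counselling. There are three routes.

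- An absolute score: "Any individuals scoring at or above the thresholds for depression recommended by [name] (6 on the PHQ-2 scale".
- A change, given directly after that score: "6 on the PHQ-2 scale), individuals whose scores have increased beyond a threshold of more than two since baseline".
- Ideation, whatever the score: "or those expressing suicidal ideation, will be contacted by phone within two days".

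Section 2.3.1 repeats the two score routes with the same figures and ties both to the PHQ-2: "those thresholds are a PHQ-2 score of six or a score increase of more than 2 relative to baseline".

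On scoring, section 8.1 says: "Scoring of the scales above follows the standardized approaches/scoring of these measures". No section prints the range or item coding of the PHQ-2. Section 8.1 lists both the PHQ-2 and the PHQ-8 for depression. The schedule in section 1.3 marks psychological wellbeing as full at baseline and after period 6, and short at the other rounds.

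Several sections describe what the rule is for. Section 7.1 says of the surveys that "they allow us to screen and refer participants with significant signs of psychological distress". Section 8.3.5 expects much depression and anxiety from baseline on. It takes these out of adverse-event reporting and says that they will be tracked and sent to counselling under the procedures already described. Section 6.5.1 describes the referral procedures as being for people in extreme distress.

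**The concern.** The rule is phrased as reaching or exceeding 6, yet on a 0–6 scale nothing exceeds 6. The change trigger might be expected to catch women below the maximum, but a woman who starts high has little room to rise. If both triggers are closed to her, she can report near-maximal symptoms at every survey without being called on the strength of those answers.

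The rule carries weight in the protocol. Section 8.3.5 substitutes it for adverse-event reporting of poor mental health, section 2.3.3 cites active monitoring and referral as a way in which psychological risk has been reduced, and section 9.4.4 plans no safety analysis. The protocol also expects high symptom levels from the outset, so women with raised baselines are not a remote case. A rule that is followed exactly and still misses such women would fall short of the purpose stated in section 7.1.

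**Working it through.** The plan gives no figure to reproduce. The check is an enumeration of a fixed rule.

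**Inputs**

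- Absolute trigger: current score s ≥ 6 (sections 2.3.1 and 8.2).
- Change trigger: s − b > 2, where b is the baseline score (same sections). On whole-number scores this means s ≥ b + 3.
- Range: two items scored 0–3, so 0–6. This is an assumption. It is taken to be what section 8.1 means by standardized scoring, but it is not printed.

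**Rule:** contact on score if s ≥ 6 or s ≥ b + 3. The lowest contacting score is the smaller of 6 and b + 3.

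| Baseline b | b + 3 | Scores firing the change trigger | Lowest contacting score | Scores with no score-based contact |
|---|---|---|---|---|
| 0 | 3 | 3–6 | 3 | 0–2 |
| 1 | 4 | 4–6 | 4 | 0–3 |
| 2 | 5 | 5, 6 | 5 | 0–4 |
| 3 | 6 | 6 | 6 | 0–5 |
| 4 | 7 (off scale) | none | 6 | 0–5 |
| 5 | 8 (off scale) | none | 6 | 0–5 |
| 6 | 9 (off scale) | none | 6 | 0–5 |

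Four results follow.

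1. The absolute trigger fires at one value, the maximum.
2. The change trigger adds something only for baselines 0, 1 and 2. At 3 it fires only at 6, which the absolute trigger already covers. From 4 upwards it cannot fire.
3. At the baseline survey the change is 0 by definition, so only a score of 6 leads to contact.
4. A woman at 5 on every survey has s = 5 < 6 and s − b = 5 − 5 = 0, which is not more than 2. Neither score trigger fires at any round. A woman who goes from 0 to 3 is called, because 3 − 0 = 3 > 2.

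**Sensitivity to coding.** If each item were coded 1–4, the range would be 2–8. Six would no longer be the maximum, the absolute trigger would fire at 6, 7 and 8, and the change trigger could fire from baselines up to 5 (8 − 5 = 3). Every woman at baseline 6 or above would already be caught by the absolute trigger. The gap would disappear, but this coding conflicts with the standardized scoring in section 8.1.

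**Sensitivity to form.** Section 8.2 does not name the scale for the change trigger. If it were read on the PHQ-8 (assumed range 0–24), it could fire from any baseline up to 24 − 3 = 21. Section 2.3.1 places the change trigger beside the PHQ-2, however, and the phone rounds are marked short, so the PHQ-2 is the natural reading.

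**The case against.** The strongest reply is that the range is not in the documents, so everything rests on an assumption. That is correct, and the assumption is stated as one. It does not remove the point: the only alternative coding considered under which the gap closes is at odds with section 8.1, and a referral rule whose meaning depends on an unprinted coding needs that coding printed.

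A second reply is that sections 2.3.1 and 8.2 agree with each other, and that a very high cut-off suits the extreme distress named in section 6.5.1. This partly stands. The two statements of the rule do not contradict one another. The mismatch is with the broader target in section 7.1 and with the reliance placed on referral in section 8.3.5. The threshold is also credited to a recommendation whose source is removed from the public text. Whether it is clinically suitable is not a matter for this review.

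Stronger readings that a reader might infer are not supported:

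- *Women at 5 are never contacted at all.* Expressed suicidal ideation leads to contact at any score, with a home visit if the woman cannot be reached by phone within 48 hours. The hotline and the open-ended question on each survey are also available, though both depend on the participant raising a concern.
- *Ideation must be volunteered.* The survey instruments are not in the documents. All that can be said is that the method of identifying ideation is not stated.
- *The lack of stopping rules rests on this referral rule.* Section 7.1 rests it on minimal risk and the freedom to decline work.
- *The rule fails most for the worst affected.* A woman at 6 at baseline is flagged at once. The gap lies at baselines 3 to 5 with later scores that stay at 5 or below.

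**Conclusion.** The concern holds in a bounded form. Under 0–6 scoring, the absolute trigger equals the scale maximum, and the change trigger is closed from baseline 4 upwards and redundant at 3. For women with baselines of 3, 4 or 5, every later score up to 5 passes without score-based contact. A woman who scores 5 throughout is never contacted on her PHQ-2 score, although expressed ideation would still bring contact.

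The conclusion rests on two readings: that standardized scoring means 0–6, and that both triggers apply to the PHQ-2. How many women fall in the gap cannot be estimated, because the documents give no baseline distribution. No estimand or analysis is affected. This is a safety procedure that, followed as written, does not serve the purpose given in section 7.1, and it should be reconciled before the main trial.

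**What to change.** - Reconcile sections 2.3.1, 6.5.1, 7.1, 8.1, 8.2 and 8.3.5 so that they describe one target group and one rule.
- State the form, item coding and score range to which 6 and the rise of more than two apply. Say which baseline score the change is measured from, given that the baseline survey is marked full and the phone rounds short.
- Have the clinical lead confirm or correct the rule so that the triggers, taken together, serve the stated screening purpose across baseline scores, including for women already high at baseline. A change trigger cannot act at the baseline survey, so the text should say what covers that visit. The choice of threshold belongs to the clinical lead, and none is proposed here.
- Before the main trial, tabulate from the pilot how many women each trigger flagged, by baseline score, and how many with high scores met neither score trigger.
- State how suicidal ideation is identified in the surveys.

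The cost is protocol wording and a tabulation of pilot data. The possible downside is more calls to the counselling provider already in place.

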8.3.5 ADVERSE EVENT REPORTING

All definitely or possibly related AEs will be immediately reported to the Principal Investigator, and then he/she will immediately inform the Institutional Review Board overseeing this project. In addition, the Principal Investigator will provide an annual summary report of all adverse events to the IRB as part of the annual review and to the Federal Agency as part of the annual Progress Report. If no adverse events have occurred, the report will state, "No adverse events affecting human subjects have occurred during this project year."

In addition to the above, please note that per NIA policy, all adverse events, regardless of their seriousness, severity or relatedness to the intervention, are reportable to the NIA PO and an independent data and safety monitoring body such as a Data and Safety Monitoring Board (DSMB) or a Safety Officer (SO), if one is appointed by NIA. Semi-annual reports (for adverse events) will be reported to NIA PO.

Note that we anticipate a large number of disease-related events given the study population. These disease-related events include diseases endemic to the area (e.g. malaria, GI distress, fevers, injuries). We do not explicitly collect data on these medical concerns as they are unrelated to the goals or likely consequences of the study and hence will only report on them as brought to our attention by study participants.

We also anticipate poor mental health (e.g. high levels of depression and anxiety from baseline onward on screening surveys). These conditions are also not considered adverse events as no diagnostic activities are completed within the study, and will not be reported in this reporting process. However, mental health outcomes will be tracked and referred to counseling, following the procedures outlined above. Suicidal thoughts reported to surveyors will be tracked and reported as an adverse event.

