The DSMB will operate under the rules of an approved charter that will be reviewed at the first DSMB meeting and approved by the members prior to the start of the trial. The DSMB will provide its input to appropriate individuals at the NIA.

Data Safety and Monitoring Board – Meeting timelines

The initial DSMB meeting will begin prior to the 400-participant pilot scheduled for May of 2024. Following that meeting, the NIH default meeting schedule for a DSMB is every 6 months. However, this study recruits participants very rapidly and those participants are then only enrolled for 3 (active) months and a one-month follow-up. After this period, there is a pause on study activities where no further participants are enrolled for eight months. Then, the process resumes. Given this timeline, the default meeting timelines every six months are ill-suited for this study.

Here instead we will plan to meet with the DSMB after sufficient data has been collected within a wave to ensure issues are identified as they arise. This allows for more timely feedback from the DSMB and, also, reduces the number of meetings with the DSMB in which no new information is available to be presented. In other words, we will arrange for the DSMB to meet once per year roughly 4 periods into the study (typically in June) during the active phase and will present information on the safety and efficacy of each arm at that time.

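### Injuries and other physical adverse events are captured passively although the protocol expects work injuries, so counts are likely too low and may not be comparable between Control and the work arms.

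*Combined protocol and SAP*

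**What the plan says.** Section 8.2, under adverse event identification, makes two statements that do not fit together. It first says "It is also likely that some workplace injuries (e.g. repetitive motion injuries) occur given the nature of the work". It expects the daily rate in treated women to be no worse than in other local work, but adds: "However, overall rates may be higher given the additional work provided". The next paragraph opens "Given that we do not anticipate any adverse events associated with participation" and gives that as the reason why "we do not aim to gather systematic data to track such events". Two routes are offered instead: a hotline for concerns about taking part, and "an open-ended question on each survey administered about any concerns about their participation".

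Other sections bear on the point:

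- Section 1.3 marks adverse event reporting at every contact. Section 8.3.4 adds events that staff learn of at visits, recorded on a case report form.
- Section 8.3.1 defines an adverse event without regard to relatedness. Section 8.3.5 states that "all adverse events, regardless of their seriousness, severity or relatedness to the intervention, are reportable to the NIA PO". It also says that disease-related events, with injuries among the examples, are not explicitly collected and are reported only if participants raise them.
- Section 7.1 anticipates no adverse events, while Section 2.3.1 accepts some injury risk from sewing.
- Section 9.4.4 (Safety Analyses) is N/A. Section 10.1.6 says of the yearly DSMB meeting that the study team "will present information on the safety and efficacy of each arm at that time".

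**The concern.** The reason given for not collecting events systematically is contradicted by the paragraph before it. The prompts also do not match the definition of what is to be counted. An adverse event counts whether or not it is related, but both prompts ask about concerns with participation. A woman who strains her wrist, or is hurt in other work, has to connect that with the study before either prompt applies to her. Control women have no study work to connect it with.

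What is at stake is the DSMB's view of physical safety, not the efficacy estimates. If few injuries are reported, the DSMB cannot tell a low rate from low capture. If the arms differ, it cannot tell a difference in risk from a difference in reporting. No table or analysis is specified that would help it do so.

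**Working it through.** **1. No figure to reproduce.** The documents give no injury rate, adverse event rate or safety sample size. The sample-size section covers efficacy endpoints only.

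**2. What is symmetric between arms and what is not.** Section 4.2 puts Control women on the same survey timeline as everyone else, and Section 8.2 places the open question on each survey. The question is therefore asked equally often in every arm. What may differ is the tendency to answer it with an injury. Treated women also have three payment contacts per two-week period (Section 5.5) at which an injury might be mentioned; Control women have none. Different capture in Control and the work arms is thus plausible, but nothing in the documents shows or measures it. The three work arms share the same prompts and payment contacts.

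**3. Illustration.** Inputs from Section 6.3: Control nC = 400; offered work nT = 400 + 400 + 1,067 = 1,867. The true risks and capture shares below are assumptions. For a two-sided test at 0.05,

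power = Φ[(|pT − pC| − 1.96·SE0)/SE1],

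with SE0 = √[p̄(1 − p̄)(1/nC + 1/nT)], p̄ the pooled observed risk, and SE1 = √[pC(1 − pC)/nC + pT(1 − pT)/nT]. Observed risk = true risk × capture share.

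*(a) Equal capture, true risk 5% in Control and 10% in the work arms.*

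- Full capture: p̄ = (20 + 186.7)/2,267 = 0.0912; SE0 = 0.01586; SE1 = 0.01292. Power = Φ[(0.05 − 0.0311)/0.01292] = Φ(1.46) = 93%.
- 30% capture in every arm: observed 1.5% and 3.0%; p̄ = (6 + 56)/2,267 = 0.0274; SE0 = 0.00899; SE1 = 0.00725. Power = Φ[(0.015 − 0.0176)/0.00725] = Φ(−0.36) = 36%.
- Power at other capture shares: 89% at 90% capture and 70% at 60% capture.

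The risk ratio stays at 2.0 throughout. Under-counting alone costs counts and power; it does not bias the comparison.

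*(b) Equal true risk, capture 30% in Control and 60% in the work arms.* The observed risk ratio is 0.60/0.30 = 2.0 although the true ratio is 1.

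| True risk, all arms | Observed Control / work | Expected counts | Chance of a false significant difference |
|---|---|---|---|
| 2% | 0.6% / 1.2% | 2.4 / 22.4 | 13% |
| 5% | 1.5% / 3.0% | 6 / 56 | 36% |
| 10% | 3.0% / 6.0% | 12 / 112 | 70% |

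**4. Reading the two together.** Case (a) at 30% capture and case (b) at a 5% true risk give the same expected data: 1.5% against 3.0%, or 6 against 56 events. In one the work doubles injuries; in the other it has no effect. Passive counts cannot separate them.

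**The case against.** The strongest reply is that this is a deliberate, explained choice in a minimal-risk study. The work is sewing at home, the expected daily injury rate is no higher than in other local work, and a duty to report known events is not a duty to solicit them. Much of that stands. It explains light-touch capture, but it does not remove the contradiction within Section 8.2 or supply the by-arm information promised to the DSMB.

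Two stronger readings are tempting, and the documents do not support them.

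- *That the hotline and open question are the only safety capture.* They are not. Section 8.3.4 adds events learned of at visits. Section 8.2 uses survey mental-health scores for safety monitoring and referral regardless of arm, and Section 8.3.5 reports suicidal thoughts as adverse events. For injuries and other physical events, though, no section describes a direct question.
- *That women are questioned differently by arm, so the arms cannot be compared.* The same question goes to all arms on the same schedule. Differential capture is a possibility, and it concerns Control against the work arms. It gives no reason to expect that an excess in high-hours periods would be hidden; there, only general under-counting applies.

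A further reply is that asking about all illness would flood the study. There are seven surveys after baseline (five during the work period, the endline and the follow-up), so 2,267 × 7 = 15,869 interviews before attrition. If 5% to 20% reported illness needing care (assumed), that is 15,869 × 0.05 = 793 to 15,869 × 0.20 = 3,174 reports to classify, taken by enumerators without medical training. This stands, and is why the item should be narrow.

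Finally, Sections 7.1 and 8.4.2 point to a separate data and safety monitoring plan, and part of Section 10.1.6 is not in the text available. By-arm reporting may be specified there. That could settle the table, but not Section 8.2's explicit decision against systematic capture.

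**Conclusion.** The point holds for injuries and other physical events. Followed as written, Section 8.2 will probably under-count the injuries it expects, and comparability between Control and the work arms cannot be assumed. That is at odds with the by-arm safety information promised in Section 10.1.6 and with N/A in Section 9.4.4.

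The size is not known, because the documents give neither injury rates nor capture shares. On assumed inputs, 30% capture in all arms lowers power for a 5% versus 10% risk from 93% to 36%. Capture of 30% against 60% gives an apparent risk ratio of 2.0 with no true difference. These figures show what passive capture could do, not what will happen. No efficacy endpoint or primary analysis is affected, and mental-health safety monitoring lies outside the point. The change is worth making because it is cheap and the gap is of the plan's own making.

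**What to change.** 1. **Section 8.2.** Replace the statement declining systematic data with one fixed closed item, added to every existing survey after baseline and worded identically in all four arms. For example: *Since the last survey, have you had any injury, including strain from work of any kind, or stayed in hospital?* The item should not mention the study or study work, so that Control women can answer it on the same footing. Keep the hotline and the open question.
2. **Section 9.4.4.** Replace N/A with a table for the DSMB giving, by arm, the number of women interviewed, the number reporting each type of event, and the number of events.
3. **Reconcile** Sections 7.1, 8.2, 8.3.5, 9.4.4 and 10.1.6 on whether adverse events are anticipated, which are collected, and what the DSMB is shown.

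The cost is a slightly longer survey, one table, and some additional reports to classify, most of them unrelated to the study. Limiting the item to injury and hospital stay, rather than all endemic illness, keeps that load small. No extra visits, staff or procedures are needed.
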